7.3.1 Reporting Special Medications

The number and percent of subjects using Crohn's disease specific medications (including corticosteroids, aminosalicylates, immunomodulators [defined as azathioprine, 6 mercaptopurine, or methotrexate], and antibiotics) within past 90 days prior to baseline (of the Study M15-993), and at baseline will be tabulated.

8.0 Patient Disposition and Study Drug Exposure

8.1 Patient Disposition

The number of subjects will be tabulated by country, investigator site and overall for the following sets: efficacy population, safety population, subjects who completed study, and subjects who prematurely discontinued study drug, as appropriate.

In addition, the number and percentage of subjects who prematurely discontinued study drug will be summarized by reason. All reasons and primary reasons for discontinuation of study drug will be summarized as recorded on the eCRF by the following categories:

- Adverse event (AE)
- Protocol violation
- Lost to follow-up
- Withdrew by subject
- Other

Subjects may have more than one reason for discontinuing study drug, but they will be counted once for the total number of premature discontinuations. Subjects have only one primary reason for discontinuing study drug or discontinuing from the study.

8.2 Study Drug Exposure and Compliance

8.2.1 Study Drug Exposure

For the safety population, the duration of exposure to study drug will be summarized. Duration of exposure of risankizumab SC is defined for each subject as number of days since first dose of risankizumab SC through min (the last risankizumab SC dose date + 56 days, the first dose date of study drug in Study M16-000 sub-Study 3). Duration of exposure of risankizumab IV is defined as number of days since first dose of risankizumab IV drug through min (the last risankizumab IV dose date + 28 days, the first dose date of risankizumab SC). Duration of exposure of all risankizumab is defined for each subject as number of days since first dose of study drug through min (the last study drug dose date + 56 days, the first dose date of study drug in Study M16-000 sub-Study 3). Study drug dose date refers to recorded dates of administration of study drug.

For each treatment group and total, the duration of exposure will be summarized by the number of subjects treated, as well as the mean, standard deviation, median, minimum and maximum values. In addition, the number and percentage of subjects exposed to study drug will be summarized for the following exclusive duration intervals:

- 1 – 84 days
- 85 – 140 days
- 141 – 196 days
- 197 – 252 days
- 253 – 308 days
- 309 – 364 days
- 365 – 420 days

421 – 476 days
477 – 532 days
533 – 588 days
589 – 644 days
645 – 700 days
701 – 756 days
757 – 812 days
813 – 868 days
869 – 924 days
> 924 days

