3. DESCRIPTION OF DESIGN AND TRIAL POPULATION

3.1 OVERALL TRIAL DESIGN AND PLAN

This open label long term extension trial investigates the long term safety and efficacy of BI 655066/ABBV-066 (risankizumab). Approximately 60 patients who meet the entry criteria are planned for inclusion in this trial, rolling over from preceding trial 1311.6. The treatment will be open label.

The treatment period will be 204 ([Flow chart 1](#)), 206 ([Flow chart 2](#)) or 216 ([Flow chart 3](#)) weeks, followed by a 140 day follow up period.

Patients rolling over from preceding trial 1311.6 will have to complete period 2 or 3 in that trial and either demonstrate a clinical response without remission at Visit E1 or a clinical response or remission at Visit E5 as defined by that protocol (see Figure 3.1:1).

[figure not shown]

Figure 3.1:1 Guideline for roll over of patients from 1311.6 to long term extension study 1311.20/M15-989

All patients directly rolled over from 1311.6 into 1311.20/M15-989 will receive 180 mg BI 655066/ABBV-066 (risankizumab) subcutaneously from visit 2 onwards every

8 weeks, until the EoT visit is performed. Patients who complete this study may elect to continue in M16-000 Sub-Study 3 (Phase 3 open label extension study).

Patients who have completed 1311.6 qualifying for roll-over into 1311.20/M15-989 before availability of this study, can be enrolled depending on their clinical remission or response. If patients were treated between finishing 1311.6 and entering 1311.20/M15-989 with anti-TNF therapy or any biologic agent an 8 weeks or 5 times the half-life (whichever is longer), wash-out period will be needed before administration of first i.v or s.c. study medication. Patients must maintain their best response status (clinical response or remission) post 1311.6. Patients who dropped from 1311.6 with remission must maintain remission or undergo re-induction while responders will have to maintain their response.

- If clinical response or remission (CDAI drop >100 from baseline of 1311.6 or CDAI < 150) was maintained after end of treatment and is confirmed at screening for 1311.20/M15-989, patients can directly be assigned to open label s.c. maintenance treatment with 180 mg every 8 weeks (FLOW CHART 1) (visit window between last IMP dose in 1311.6 and first IMP dose in 1311.20/M15-989 should be at least 8 weeks).

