- If clinical remission (achieved at E5 1311.6) has been lost after end of treatment in 1311.6 and/or at screening for 1311.20/M15-989, patients will receive open label i.v. re-induction treatment with three infusions of 600 mg each every 4 weeks after which eligibility will be re-assessed. If clinical remission or at least response compared to 1311.6 study baseline (V2) is achieved patients will switch to s.c. maintenance treatment with 180 mg s.c. every 8 weeks ([Flow chart 3](#)), otherwise an EoT visit has to be performed. After last administration of trial drug in 1311.20/M15-989 trial, a 140 day follow up call should be scheduled for patients who do not elect to enroll in Study M16-000.
- If clinical response (achieved at E1 or E5 1311.6) has been lost after end of treatment in 1311.6 and/or at screening for 1311.20/M15-989, patients will receive open label i.v. re-induction treatment with three infusions of 600 mg each every 4 weeks after which eligibility will be re-assessed. If clinical response or remission compared to 1311.6 study baseline (V2 1311.6) is achieved patients will switch to s.c. maintenance treatment with 180 mg s.c. every 8 weeks ([Flow chart 3](#)), otherwise an EoT visit has to be performed. After last administration of trial drug in 1311.20/M15-989 trial, a 140 day follow up call should be scheduled for patients who do not elect to enroll in Study M16-000.

The results from the last colonoscopy done in 1311.6 will serve as baseline for 1311.20/M15-989. A colonoscopy at screening is only required for patients who lost

response or remission during extended follow-up phase after completion of 1311.6. Colonoscopies are repeated once per year to assess the effect of continued treatment on endoscopic response and mucosal healing.

The end of study is defined as the date the last subject completes the End of trial visit

The primary analysis will be performed after all patients have completed their EoT visit. The reference values for the efficacy endpoints clinical or endoscopic response will be the baseline values in 1311.6.

For details regarding Adverse event and serious adverse event reporting, see [Section 5.2.2.2](#)

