6.4 Definition of Visit Windows

Since subjects do not always adhere to the study visit schedule, the following rules will be applied to assign actual visits to protocol-specified visits including early termination visits. For each study visit mentioned in the protocol, a nominal or target day will be selected to represent the corresponding visit along with a window around the target day. Windows will be selected in a non-overlapping fashion so that a date collected on the case

report form (CRF) does not correspond to multiple visit windows. Moreover, windows will not discard any post-baseline measurement recorded on the CRF. If a subject had 2 or more actual visits in one visit window, the visit closest to the target will be used as the study visit for that window. If two visits are equidistant from the target day, then the later visit will be used for reporting.

The visit windows and the target/nominal day for each study visit are shown in the tables below. The visit windows defined below will be based on relative days to either first dose on IV or first dose on SC.

Table 1. Windows for subcutaneous injection period for ITT_SC (SA_SC) population, using for Vital sign, Lab Values, Fistula exam, CDAI, Review patient diary (PRO data).

Nominal Visit Week^d	Lower Bound	Nominal Day	Upper Bound
0	-999	1 ^a	1
8	2	57	85
X ^c	$1 + 7*(X - 4) + 1$	$1 + 7*X$	$1 + 7*(X + 4)$
200	1374	1401	9999 ^b

- a. Day of first dose of study drug for subcutaneous injection.
- b. It is minimum of (the last dose date + 140 days, the first dose date of Study M16-000 sub-Study 3) for the subjects who entered the Study M16-000 sub-Study 3; otherwise it is the last dose date +140 days.
- c. $X = 8*i$, $i = 2, \dots, 24$.
- d. Nominal visit week is a transformation of the protocol-specified week. For the patients' schedule following the Flow Chart 1, nominal visit week = protocol-specified week – 4. For the patients' schedule following the Flow Chart 2, nominal visit week = protocol-specified week – 6. For the patients' schedule following the Flow Chart 3 (only for subcutaneous injection period), nominal visit week = protocol-specified week – 16.

Table 2. Windows for subcutaneous injection period for ITT_SC population, using for CDEIS and SES-CD.

Nominal Visit Week ^c	Lower Bound	Nominal Day	Upper Bound
0	-999	1 ^a	1
48	2	337	533
104	534	729	897
152	898	1065	1233
200	1234	1401	9999 ^b

- a. Day of first dose of study drug for subcutaneous injection.

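### All-risankizumab exposure in SAP 8.2.1 credits 28 days more than the IV column when the last dose was an infusion, and the duration classes stop at 924 days

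*SAP*

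**What the plan says.** SAP 8.2.1 defines three exposure durations for the safety population:

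- **IV:** from the first infusion to "min (the last risankizumab IV dose date + 28 days, the first dose date of risankizumab SC".
- **SC:** from the first injection to "min (the last risankizumab SC dose date + 56 days, the first dose date of study drug in Study M16-000 sub-Study 3".
- **All risankizumab:** the "number of days since first dose of study drug through min (the last study drug dose date + 56 days", with the first M16-000 Sub-Study 3 dose as the other limit. The route of the last dose plays no part.

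Each duration is summarised by number treated, mean, SD, median, minimum and maximum. It is also tabulated in classes: 1–84 days, then 56-day steps up to 869–924 days, then one open class for everything longer.

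Protocol 3.1 foresees patients whose last dose is an infusion. Those who lost response or remission receive "re-induction treatment with three infusions of 600 mg each every 4 weeks after which eligibility will be re-assessed". If response is regained they move to SC maintenance, "otherwise an EoT visit has to be performed".

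On planned length, Protocol 3.1 states "The treatment period will be 204" weeks for Flow Chart 1, 206 for Flow Chart 2 and 216 for Flow Chart 3. SAP 6.4 puts the three schedules on one SC time scale by subtracting 4, 6 and 16 weeks, and its visit windows run to SC week 200.

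**The concern.** The IV and SC rules each credit a dose with its own dosing interval: 28 days for an infusion and 56 days for an injection. The pooled rule departs from this when the last dose is an infusion. Two columns of one table then give different exposure for the same patient and the same doses, and no reason is stated.

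The class table has a different weakness. It resolves early exposure in 56-day steps and then stops at 924 days, well short of the planned length. The primary objective is long-term safety, so the number of patients with about three or three and a half years of exposure is a natural thing to want from this table.

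**Working it through.** The documents state no resulting exposure figure to reproduce. As a check on the schedule, the SAP's nominal day for SC week 200 does reproduce: 1 + 7 × 200 = 1401 (SAP 6.4, Table 1).

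**Inputs.** Infusions at weeks 4, 8 and 12 (Flow Chart 3). First SC dose at week 4, 6 or 16 and last at week 204, 206 or 216 (Flow Charts 1, 2 and 3). Tails of 28 days (IV), 56 days (SC) and 56 days (pooled), from SAP 8.2.1.

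**Formula.** Exposure = (last dose week − first dose week) × 7 + tail, as a date difference, assuming no M16-000 dose within the tail.

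**Patient who receives only the three infusions**

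- First to last infusion: (12 − 4) × 7 = 56 days.
- IV column: 56 + 28 = 84 days.
- Pooled column: 56 + 56 = 112 days.
- Difference: 28 days, or 28/84 = 33% of this patient's IV figure.
- Counting both end days gives 85 and 113 days. The difference is again 28.
- With the visit windows (±7 days for the first infusion, ±5 for the third) the span moves by up to 12 days either way. The ranges become 72–96 and 100–124 days.
- A patient stopping after one or two infusions shows the same 28-day gap: 28 against 56, or 56 against 84.

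**Patient who goes from IV to SC on schedule**

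- IV: 84 days, because last infusion + 28 days falls on the first SC dose at week 16.
- SC: (216 − 16) × 7 + 56 = 1456 days.
- Pooled: (216 − 4) × 7 + 56 = 1484 + 56 = 1540 = 84 + 1456. The rules agree, so the mismatch arises only when the last dose is an infusion.

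**Same infusion-only patient in the event-rate denominator (SAP 10.2.1.7)**

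- IV and pooled patient-time both end 140 days after the last infusion: 56 + 140 = 196 days in each. There is no mismatch.

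**Duration classes**

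- 924 days = 132 weeks; 924/365.25 = 2.5 years.
- Planned completer, Flow Charts 1 and 2: 200 × 7 + 56 = 1456 days; 1456/365.25 = 4.0 years.
- SC doses every 8 weeks from SC week 0 to 200: 200/8 + 1 = 26.
- 16th SC dose: 15 × 56 + 56 = 896 days, inside 869–924. 17th: 16 × 56 + 56 = 952 days, in the open class. Last doses 17 to 26 therefore share one class.
- In the pooled column a re-induced patient starts 84 days earlier and reaches the open class with the 16th SC dose: 84 + 15 × 56 + 56 = 980 days.
- Planned range inside the open class: 1456 − 924 = 532 days (37% of 1456), or 1540 − 924 = 616 days (40% of 1540).

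**The case against.** The strongest reply is that no stated figure is wrong. The SAP gives three explicit definitions for three groups, and both 28 and 56 days are conventions. Protocol 5.2.2.2 treats a patient as on treatment for 20 weeks after the last dose whatever the route, so neither 84 nor 112 days is true exposure. That stands. A reader might infer that early failures are shown with more exposure than they had, but the documents support only that two columns of one table follow different conventions.

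A reader might also infer that the safety rates are distorted. They are not. Rates per 100 patient-years (SAP 10.2.1.7) and the treatment-emergent window (SAP 10.2.1) have their own 140-day rules, and the percentages count patients.

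Nor does the same patient necessarily fall in two classes. By date difference 84 and 112 days lie in 1–84 and 85–140. Under inclusive counting, which SAP 6.3 uses for Rx days but 8.2.1 does not mention, 85 and 113 share the class 85–140.

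The effect on the pooled total is small. Assume 1 to 10 infusion-only patients among 60, with the others averaging 728 to 1456 days. The excess then runs from 28/(59 × 1456 + 84) = 0.03% to 280/(50 × 728 + 840) = 0.75%.

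On the classes, the Amendment 4 entry in Protocol Section 11 says the study will be terminated, with patients ending at different times. One cannot infer that any given number will pass 924 days. Mean, median and range, injection counts, cumulative dose and by-visit summaries to SC week 200 also remain. What survives is that this table cannot show the distribution above 924 days, and unequal durations make such a distribution more useful.

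**Conclusion.** Both points hold as minor defects of one descriptive table.

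First, when the last dose is an infusion, the pooled column credits 28 days more than the IV column. The 28-day gap does not depend on the counting convention or on the visit windows. It does assume no M16-000 dose within 56 days of the last infusion. The number of patients affected is not given and is probably small.

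Second, in the SC and all-risankizumab columns the classes cannot separate exposures between about 2.5 and 4 years. The IV column is not concerned, since planned IV exposure is about 84 days. How much this matters depends on how many patients passed 924 days before the early close, which the documents do not say.

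Neither point reaches the event rates, the treatment-emergent definition or any efficacy result.

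**What to change.** In SAP 8.2.1, end all-risankizumab exposure at last dose + 28 days if that dose was IV and + 56 days if it was SC, keeping the cap at the first M16-000 Sub-Study 3 dose. State whether day counting is inclusive. The infusion-only patient on schedule then counts 84 days (or 85) in both columns, and figures for patients whose last dose is SC do not change.

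For the classes, either continue the 56-day steps or add cumulative rows for at least 1, 2, 3 and 3.5 years. Eleven more steps reach 1540 days ((1540 − 924)/56 = 11), the longest planned exposure by date difference; a final open class would catch late visits. The cumulative rows are shorter and answer the long-term question directly.

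The cost is a changed definition, one sentence on counting and a longer table shell. No new data are needed. Pooled exposure becomes slightly lower for patients whose last dose was an infusion. This is a reporting convention and touches no dosing or clinical rule.

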8.2.2 Study Drug Compliance

The treatment compliance (%) of risankizumab dose information will be summarized for safety population:

8.2.2.1 Intravenous Therapy

Total number of infusions received
Cumulative risankizumab dose (mg)

8.2.2.2 Subcutaneous Therapy

Total number of injections received
Cumulative risankizumab dose (mg)

9.0 Efficacy Analysis

9.1 General Considerations

There is no formal statistical hypothesis test planned. Descriptive analyses will be used to analyze the proportion of participants achieving the efficacy endpoints. The study is designed to gain extensive documentation of safety and efficacy.

9.1.1 Analysis of Efficacy Endpoints by Variable Type**9.1.2 Missing Data Imputation for Efficacy Endpoints**

Missing data imputation will be done only for categorical efficacy variables. For the analysis other than efficacy, no imputation will be done for missing values.

Non-Responder Imputation (NRI)

The NRI approach is used for binary efficacy variables. These variables can take values of 'Achieved' or 'Not Achieved' or may be missing for any reason including discontinuation from study. According to the NRI imputation approach, all missing values will be considered as 'Not Achieved.' If a subject has missing value for a specific visit, the data will be imputed using NRI only for the period which the visit belongs to.

Observed Case (OC)

Observed case analysis will be performed, i.e., missing values will not be imputed. An analysis using only the observed data will be performed as a sensitivity analysis for primary and secondary efficacy endpoints.

Imputation of Missing Dates

For baseline, efficacy, and safety parameters, if the day and/or month are missing, the following conventions will be used to impute the missing dates:

- 01 for missing start day
- End of month for missing end day
- January 1st for missing start month
- December 31st for missing end month

In case of partially missing AE start and stop dates, the dates will be imputed by comparing to first dose date of study medication so that the corresponding AEs will be made treatment-emergent whenever possible. If the start date of an AE is partially

missing and the month is the same as the start date of a new therapy, the AE will be made treatment emergent to the new therapy.

In case of missing or partially missing study drug dosing dates, the dates will not be imputed. Subjects will be treated as not receiving dose on that date.

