5.0 Analysis Populations

5.1 Definition of Analysis Populations

5.1.1 Efficacy Populations

Intent-to-Treat Analysis Set

The Intent-to-Treat Analysis Set (ITT) includes all subjects who received at least one dose of risankizumab in the current study.

- The Intent-to-Treat Analysis Set for IV (ITT_IV) includes all subjects who received at least one dose of risankizumab IV in the current study.
- The Intent-to-Treat Analysis Set for SC (ITT_SC) includes all subjects who received at least one dose of risankizumab SC in the current study.

The ITT population will primarily be used for all efficacy analyses. Any by-period analyses on IV (or SC treated population) will be based on ITT IV set (or ITT SC set).

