5.2 Definition of Treatment Groups

The treatment groups for efficacy analysis are as below:

During IV period: Risankizumab 600 mg IV

During SC period: Risankizumab 180 mg SC

The treatment groups for safety analysis are as below:

During IV period: Risankizumab 600 mg IV

During SC period: Risankizumab 180 mg SC

During the current study: All Risankizumab

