Particularly, a concomitant medication for IV period should have the start date before the date of last dose of study drug in IV period plus 140 days or the date of the first dose in SC period, whichever occurs earlier. A concomitant medication for SC period should have the start date before the date of last dose of study drug in SC period plus 140 days or the date of the first dose in Study M16-000 sub-Study 3 if any, whichever occurs earlier.

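### SAP 9.1.2 does not say whether visits never due after roll-over or sponsor termination are missing; read literally, non-responder imputation scores them as failures

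*SAP*

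**What the plan says.** **Imputation.** SAP 9.1.2 applies NRI to binary efficacy variables, whose values "may be missing for any reason including discontinuation from study". It then says: "According to the NRI imputation approach, all missing values will be considered as 'Not Achieved". The only limit is that "the data will be imputed using NRI only for the period which the visit belongs to". For efficacy, SAP 5.2 names an IV and an SC period ("During SC period: Risankizumab 180 mg SC") and gives neither an end date. SAP 12.2 adds that patients who discontinue before a diary endpoint, whatever the reason, count as not achieving it. Protocol 7.4, by contrast, says missing data are not imputed.

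**Denominator and grid.** The SC efficacy set "includes all subjects who received at least one dose of risankizumab SC in the current study" (SAP 5.1.1). SAP 6.4 runs the visit windows to nominal Week 200.

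**Observed cases.** SAP 9.1.2 says: "An analysis using only the observed data will be performed as a sensitivity analysis for primary and secondary efficacy endpoints". SAP 9.3 and 9.5 use both OC and NRI without ranking them.

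**End of participation.** Protocol 3.1, the flow-chart footnotes and SAP 4.2 let patients who complete EoT enter M16-000 Sub-Study 3. The flow charts give EoT no week number. The Amendment 4 rationale (protocol section 11) says that the study will be terminated and that patients will stop at different weeks. Protocol 3.1 nevertheless still gives treatment periods of 204, 206 or 216 weeks.

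**Roll-over elsewhere in the SAP.** SC-period concomitant medication is limited by "the date of the first dose in Study M16-000 sub-Study 3 if any, whichever occurs earlier" (SAP 7.3). Exposure (8.2.1), treatment-emergent events (10.2.1) and patient-years (10.2.1.7) also stop at the first M16-000 dose. For patients who transfer, the upper bound of the last visit window is described so: "It is minimum of (the last dose date + 140 days, the first dose date of Study M16-000 sub-Study 3".

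**The concern.** The SAP closes its safety and exposure accounting when a patient moves to M16-000, but its imputation rule has no matching sentence. A patient who is in remission at EoT and then transfers has no later data in this study. Combining the words on all missing values, the fixed SC set and the Week 200 grid makes that patient a failure at every later visit.

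Protocol 3.2 names early evidence on the durability of response as a goal, and by-visit rates are where a reader will look for it. Late NRI rates would then mix loss of response with the timing of roll-over. The rule reaches 16 endpoints: 10 of the 20 secondary endpoints in SAP 4.3.2 are binary, and so are all 6 exploratory endpoints in 4.3.3.

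**Working it through.** **1. The grid.** The documents give no sample-size or power figure on this point, so the visit grid is what can be reproduced. Flow Charts 1, 2 and 3 give 204 − 4 = 206 − 6 = 216 − 16 = Week 200. Its target day is 1 + 7 × 200 = 1401 and its window opens on 1 + 7 × 196 + 1 = day 1374, both as in SAP Table 1. There are 25 post-baseline SC visits for CDAI and PRO-2.

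**2. Visits left empty: an example.** Take EoT on SC day 701, the last day of the Week 96 window (target 673 + 28).
- CDAI/PRO-2: Week 104 opens on 7 × 100 + 2 = day 702, so Weeks 104 to 200 are empty: 13 of 25.
- Endoscopy (Table 2): windows open on days 2, 534, 898 and 1234, so 2 of 4 have not opened.
- IBDQ (Table 3): windows open on days 2, 254, 422, 590, 758, 926, 1094 and 1262, so 4 of 8 have not opened.

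**3. Effect on the rate.** Let p be the NRI rate among patients still due and a the share of the SC set ended administratively before the visit. The literal rule reports p(1 − a). Both inputs are assumed.

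| p | a = 25% | a = 50% | a = 75% |
|---|---|---|---|
| 50% | 37.5% | 25% | 12.5% |
| 70% | 52.5% | 35% | 17.5% |
| 90% | 67.5% | 45% | 22.5% |

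A 10-point shortfall needs a = 0.10/p. At p = 70% that is 14.3%, or 0.143 × 60 = 8.6, about 9 patients if all 60 planned enter the SC set.

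**4. Where the full-cohort rate could lie.** If transferred patients would have had rate q, the full-cohort rate is p(1 − a) + qa. All-missing NRI is the case q = 0, so it is the lower limit. At p = 70% and a = 50% the range is 35% to 85%.

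**5. OC is a different quantity.** Assume 80% success among observed values, 10% of due values missing, and a = 50%. OC gives 80%, NRI among patients due gives 0.80 × 0.90 = 72%, and literal NRI gives 72% × 0.50 = 36%. Neither planned table shows the middle figure.

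**6. The period clause.** SAP 10.2.1.7 dates the SC period, for patient-years, to the earlier of last SC dose + 140 days and the first M16-000 dose. Borrowed for efficacy, those limits would exempt transferred patients and also those stopping at termination without transfer. They would equally exempt ordinary dropouts once 140 days had passed, although 9.1.2 expressly includes discontinuation.

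**The case against.** **A visit that was never due is not missing.** This is the strongest reply. SAP 9.1.2 and 12.2 speak of discontinuation, roll-over follows completion, and SAP 8.1 counts completers apart from premature discontinuations. A reader might infer that the SAP definitely counts completers as failures, or that the tables were produced that way. The documents support neither: they do not say whether such a visit is missing, and they do not show the programming. What stands is that two programmers could produce different tables from the same text.

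**The period clause already handles it.** It can be read so, but only with limits taken from a patient-year rule that conflict with 9.1.2 on dropouts. The window footnote does not help: it caps which data enter the last window, not who is in the denominator.

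**NRI is not the leading analysis.** It would be tempting to say that it is. The sensitivity label on OC covers primary and secondary endpoints only and does not reach the exploratory ones. SAP 9.3 and 9.5 rank neither method, and protocol 7.4 points away from imputation. This part of the reply stands. OC still does not repair the gap, because it also drops patients who left after failing.

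**The stakes are small.** Safety is the primary objective, and efficacy has no test and no primary analysis. This limits severity.

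**Removing elective transfers selects patients.** This also stands. If q is below p, the restricted rate is too high by a(p − q): with p = 70%, q = 50% and a = 50%, by 10 points.

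**Conclusion.** The point holds as a gap in the rule as written, with medium confidence. Taken literally with the SC set and the Week 200 grid, SAP 9.1.2 scores never-due visits as failures. Nothing in the SAP clearly prevents this, although roll-over was foreseen.

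The size is p(1 − a), so each 10% of the SC set ended administratively lowers the reported rate by 10% in relative terms with no patient losing response. How large that was cannot be known from the documents, which give no roll-over counts, dates or response rates. The importance is moderate and confined to descriptive NRI tables: it warrants a wording change but does not affect the safety conclusions.

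Two related inconsistencies should be settled with it: NRI in the SAP against no imputation in protocol 7.4, and the fixed treatment periods in protocol 3.1 against the undated EoT column and the Amendment 4 rationale.

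**What to change.** In SAP 9.1.2:

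- When EoT results from roll-over to M16-000 or sponsor termination, apply NRI only to visits whose target day falls on or before EoT. Later visits without data are not imputed, and the patient leaves that visit's NRI denominator.
- Keep NRI for in-study gaps and all other discontinuations.
- Show the number due at each visit, with all-missing NRI and OC alongside.
- Tabulate response status at EoT for transferred patients, since transfer is elective and may be related to response.
- Name the record that identifies sponsor-terminated patients who do not transfer; the reasons listed in SAP 8.1 have no such category.
- Explain the departure from protocol 7.4.

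Align SAP 12.2 so that discontinuing excludes these completers, and reconcile the duration statements in protocol 3.1.

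Target day is safer than window opening. The Week 104 endoscopy window opens on day 534 for a target of day 729, so a rule based on opening would fail a patient who rolled over on day 540 without endoscopy, 729 − 540 = 189 days before the visit was due.

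**Cost.** SAP wording and some programming; no new visits or data. Late denominators shrink: 21 of 30 has an exact 95% interval of about 51% to 85%. The restricted rate is too high if transferred patients were doing worse, which is why all-missing NRI and the EoT table are kept. A patient whose EoT endoscopy falls in a window before its target day still contributes that value, while one without it does not, so the count of each should be shown.
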